3.2.2.2 Exclusion criteria

Patients eligible for enrollment into the treatment phase of this study **must not meet any** of the following criteria:

- 1. Patients who have received prior treatment with a P13K inhibitor
- 2. Patients with a known hypersensitivity to buparlisib or to its excipients
- 3. Patients with untreated brain metastases are excluded. However, patients with metastatic CNS tumors may participate in this trial, if the patient is > 4 weeks from therapy completion (incl. radiation and/or surgery), is clinically stable at the time of study entry and is not receiving corticosteroid therapy
- 4. Patients with acute or chronic liver, renal disease or pancreatitis
- 5. Patients with baseline creatinine kinase (CK) > upper limit of normal (ULN)
- 6. Patients with the following mood disorders as judged by the Investigator or a psychiatrist, or as a result of patient's mood assessment questionnaire:
 - •• Medically documented history of or active major depressive episode, bipolar disorder (I or II), obsessive-compulsive disorder, schizophrenia, a history of suicidal attempt or ideation, or homicidal ideation (immediate risk of doing harm to others)
 - ◆◆ ≥ CTCAE Grade 3 anxiety
 - Meets the cut-off score of ≥ 12 in the PHQ-9 or a cut-off of ≥ 15 in the GAD-7 mood scale, respectively, or selects a positive response of "1, 2, or 3" to question number 9 regarding potential for suicidal thoughts in the PHQ-9 (independent of the total score of the PHQ-9)
- 7. Patients with diarrhea \geq CTCAE Grade 2
- 8. Patient has active cardiac disease including any of the following:
 - ◆◆ Persistent Left ventricular ejection fraction (LVEF) < 50% as determined by prior Multiple Grated acquisition (MUGA) scan or echocardiogram (ECHO)
 - ◆◆ QTc > 450 msec on screening ECG (using the QTcF formula)
 - ♦♦ Angina pectoris that requires the use of anti-anginal medication
 - ◆◆ Ventricular arrhythmias except for benign premature ventricular contractions
 - ◆◆ Supraventricular and nodal arrhythmias requiring a pacemaker or not controlled with medication
 - **♦♦** Conduction abnormality requiring a pacemaker
 - ◆◆ Valvular disease with document compromise in cardiac function
 - **♦♦** Symptomatic pericarditis
- 9. Patient has a history of cardiac dysfunction including any of the following:
 - ◆◆ Myocardial infraction within the last 6 months, documented by persistent elevated cardiac enzymes or persistent regional wall abnormalities on assessment of LVEF function
 - ◆◆ History of documented congestive heart failure (New York Heart Association functional classification III-IV)
 - **♦♦** Documented cardiomyopathy

- 10. Patient has poorly controlled diabetes mellitus (defined as HgA1c > ULM), steroid-induced diabetes mellitus or insulin dependent diabetes mellitus.
- 11. Other concurrent severe and/or uncontrolled concomitant medical conditions (eg, active or uncontrolled infection) that could cause unacceptable safety risks or compromise compliance with the protocol
- ◆◆ Significant symptomatic deterioration of lung function. If clinically indicated, pulmonary function tests including measures of predicted lung volumes, DLco, O2 saturation at rest on room air should be considered to exclude pneumonitis or pulmonary infiltrates.
- 12. Impairment of gastrointestinal (GI) function or GI disease that may significantly alter the absorption of buparlisib (eg, ulcerative diseases, uncontrolled nausea, vomiting, diarrhea, malabsorption syndrome, or small bowel resection). Patients with unresolved diarrhea will be excluded as previously indicated
- 13. Patients who have been treated with any hematopoietic colony-stimulating growth factors (eg, G-CSF, GM-CSF) ≤ 2 weeks prior to starting study drug. Erythropoietin or darbepoetin therapy, if initiated at least 2 weeks prior to enrollment, may be continued.
- 14. Patients who are currently receiving treatment with medication with a known risk to prolong the QT interval or inducing Torsades de Pointes and the treatment cannot either be discontinued or switched to a different medication prior to starting study drug. Please refer to Table 16 for a list of prohibited QT-prolonging drugs with risk of Torsades de Pointes.
- 15. Patients receiving chronic treatment with steroids or another immunosuppressive agent.
 - Note: Topical applications (eg, rash), inhaled sprays (eg, obstructive airways diseases), eye drops or local injections (eg, intr-articular) are allowed. Oral or systemic liver enzyme inhibitors such as topical antifungal creams are allowed. Patients with previously treated brain metastases, who are on stable low dose corticosteriods treatment (eg, dexamethasone 2 mg/day, predisolone 10 mg/day) for at least 14 days before start of study treatment are eligible.
- 16. Patients who have taken herbal medications and certain fruits within 7 days prior to starting study drug. Herbal medications include, but are not limited to St. John's Wort, Kava, and ephedra (ma huang), dehydroepiandrosterone (DHEA), gingko biloba, yohimbe, saw palmetto, and ginseng. Fruits include the CYP3A inhibitors Seville oranges, grapefruit, pummelos, or exotic citrus fruits.
- 17. Patients who are currently treated with drugs known to be moderate and strong inhibitors or inducers of isoenzyme CYP3A, and the treatment cannot be discontinued or switched to a different medication prior to starting study drug. Please refer to Table 15 for a list of prohibited inhibitors and inducers of CYP3A (Please note that co-treatment with weak inhibitors of CYP3A is allowed).
- 18. Patients who have received chemotherapy or targeted anticancer therapy ≤ 4 weeks (6 weeks for nitrosourea, antibodies or mitomycin-C) prior to starting study drug must recover to a Grade 1 before starting the trial
- 19. Patients who have received any continuous or intermittent small molecule therapeutics (excluding monoclonal antibodies) ≤ 5 effective half-lives prior to starting study drug or who have not recovered from side effects of such therapy
- 20. Use of statin drugs or other medications known to associate with rhabdomyolysis. These drugs must be discontinued at enrollment.

- 21. Patients who have received wide field radiotherapy ≤ 4 weeks or limited field radiation for palliation ≤ 2 weeks prior to starting study drug or who have not recovered from side effects of such therapy
- 22. Patients who have undergone major surgery ≤ 2 weeks prior to starting study drug or who have not recovered from side effects of such therapy.
- 23. Patients who are currently taking therapeutic doses of warfarin sodium or any other coumadin-derivative anticoagulant. Low molecular weight heparin is allowed.
- 24. Women who are pregnant or breast feeding or adults of reproductive potential not employing an effective method of birth control. Double barrier contraceptives must be used through the trial by both sexes. Oral, implantable, or injectable contraceptives may be affected by cytochrome P450 interactions, and are therefore not considered effective for this study. Women of child-bearing potential, defined as sexually mature women who have not undergone a hysterectomy or who have not been naturally postmenopausal for at least 12 consecutive months (ie, who has had menses any time in the preceding 12 consecutive months), must have a negative serum pregnancy test ≤ 72 hours prior to initiating treatment.
 - ♦♦ Women are considered post-menopausal and not of child bearing potential if they have had 12 months of natural (spontaneous) amenorrhea with an appropriate clinical profile (eg, age appropriate, history of vasomotor symptoms) or six months of spontaneous amenorrhea with serum FSH levels > 40 mIU/mL (for US only: and estradiol < 20 pg/mL) or have had surgical bilateral oophorectomy (with or without hysterectomy) at least six weeks ago. In the case of oophorectomy alone, only when the reproductive status of the woman has been confirmed by follow up hormone level assessment is she considered not of child bearing potential.
 - •• Women of child-bearing potential, defined as all women physiologically capable of becoming pregnant, must use highly effective contraception during the study and through 20 months after the final dose of study treatment. For males with partners with childbearing potential, highly effective contraception is required for 6 months. The highly effective contraception is defined as either:
- I. True abstinence: When this is in line with the preferred and usual lifestyle of the subject. Periodic abstinence (eg, calendar, ovulation, symptothermal, post-ovulation methods) and withdrawal are not acceptable methods of contraception.
- II. Sterilization: have had surgical bilateral oophorectomy (with or without hysterectomy) or tubal ligation at least six weeks ago. In case of oophorectomy alone, only when the reproductive status of the woman has been confirmed by follow up hormone level assessment.
- III. Male partner sterilization (with the appropriate post-vasectomy documentation of the absence of sperm in the ejaculate). For female subjects on the study, the vasectomised male partner should be the sole partner for that patient.
- IV. Use of a combination of any two of the following (a+b):
 - a. Placement of an intrauterine device (IUD) or intrauterine system (IUS)
 - b. Barrier methods of contraception: Condom or Occlusive cap (diaphragm or cervical/vault caps) with spermicidal foam/gel/film/cream/vaginal suppository

- •• Oral contraception, injected or implanted hormonal methods are not allowed as buparlisib potentially decreases the effectiveness of hormonal contraceptives.
- ◆◆ Fertile males, must use highly effective (double barrier) methods of contraception (eg, spermicidal gel plus condom) for the entire duration of the study, and continuing using contraception and refrain from fathering a child for 6 months following the study drug. A condom is required to be used also by vasectomized men as well as during intercourse with a male partner in order to prevent delivery of the study treatment via seminal fluid. Female partner of male study subject should use highly effective contraception during dosing of any study agent and for 16 weeks after final dose of study therapy.

Note: Hormonal contraception methods (eg, oral, injected, implanted) are not allowed as it cannot be ruled out that the study drug decreases the effectiveness of hormonal contraception.

Note: Woman are considered post-menopausal and not child bearing potential if they have had 12 months of natural (spontaneous) amenorrhea with an appropriate clinical profile (eg, age appropriate, history of vasomotor symptoms) or six months of spontaneous amenorrhea with serum FSH levels > 40 mIU/ mL and estradiol < 20 pg/mL or have had surgical bilateral oophorectomy (with or without hysterectomy) at least six weeks ago. In the case of oophorectomy alone, only when the reproductive status of the woman has been confirmed by follow up hormone level assessment is she considered not of child bearing potential

- 25. Known diagnosis of human immunodeficiency virus (HIV) infection, Hepatitis B or Hepatitis C
- 26. History of another malignancy within 3 years, except cured basal cell carcinoma of the skin or excised carcinoma in situ of the cervix
- 27. Patient is unable or unwilling to abide by the study protocol or cooperate fully with the investigator

4 Treatments

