Grade 2	CT scan with lung windows. Consider pulmonary function testing includes: spirometry, DLco, and room air O₂ saturation at rest. Repeat at least every 8 weeks until return to within normal limits. Consider a bronchoscopy with biopsy and / or BAL.	Symptomatic only. Consider corticosteroids if symptoms are troublesome.	Reduce buparlisib dose 50% (see Table 10) until recovery to ≤ Grade 1. Study treatment may also be interrupted if symptoms are troublesome. Patients will discontinue study treatment if they fail to recover to ≤ Grade 1 within 3 weeks.

Grade 3	CT scan with lung windows and pulmonary function testing includes: spirometry, DLco, and room air O ₂ saturation at rest. Repeat at least every 6 weeks until return to within normal limits. Bronchoscopy with biopsy and / or BAL is recommended.	Consider corticosteroids if infective origin is ruled out. Taper as medically indicated.	Hold treatment with buparlisib until recovery to ≤ Grade 1. May restart study treatment within 3 weeks at a 50% dose reduction if evidence of clinical benefit.
Grade 4	CT scan with lung windows and required pulmonary function testing, if possible, includes: spirometry, DLco, and room air O ₂ saturation at rest. Repeat at least every 6 weeks until return to within normal limits. Bronchoscopy with biopsy and / or BAL is recommended if possible.	Consider corticosteroids if infective origin is ruled out. Taper as medically indicated.	Discontinue treatment with buparlisib.

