4.2.3.2 Drugs to be used with caution

Preliminary in vitro metabolism studies suggest that buparlisib is a weak, reversible inhibitor CYP3A4/5 (Ki=13.6 μM, [I]/Ki= 0.4 where [I] is the average C_{max} at steady-state following 100 mg daily dose) and a weak reversible inhibitor of CYP2C8/2C9/2C19 (IC₅₀=34 μM, [I]/IC₅₀=0.15). Note: that with the data available, we are not able to confirm whether such interactions will occur in patients. Therefore, investigators, at their discretion, may administer concomitant medications known to be metabolized by CYP3A4/5, CYP2C8, CYP2C9 and CYP2C19. Patients receiving such medications must be carefully monitored for potentiation of toxicity due to any individual concomitant medications, and may require dose titration or reduction of the drug substrate. Please refer to Table 17 for a list of CYP450 substrates and carefully consider their co-administration with buparlisib.

Particularly, caution is advised when buparlisib is coadministered with:

- ◆◆ Drugs which are substrates for CYP3A4, CYP2C8, CYP2C9 or CYP2C19 and which have a narrow therapeutic index.
- ◆◆ Oral anti-diabetics which are metabolized by CYP2C8 or CYP2C9 can possibly result in hypoglycemia. Patients who develop diabetes mellitus during the study should be treated according to the American Diabetes Association guidance. It is recommended that treatment start with metformin.
- ♦♦ If a patient, after study enrollment, requires the concomitant use of any QT prolonging medication with a possible or conditional risk for torsade de pointes then the investigators, at their discretion, may co-administer such medications. Patients receiving such medications must be monitored. Refer to Table 16 for a list of QT-prolonging medications to be used with caution.

Note: please refer also to Table 16 for a list of prohibited QT prolonging medication.

- ◆◆ Please refer to Table 17 for a list of CYP450 substrates and carefully consider their co-administration with buparlisib.
- ♦♦ Concomitant treatment with corticosteroids and buparlisib should be avoided, whenever possible, during this study. A short duration (< 2 weeks) of systemic corticosteroids is allowed (eg, for chronic obstructive pulmonary disease, or as an anti-emetic). Chronic dosing of corticosteriods is known to induce CYP3A enzymes, thereby increasing the risk or reducing buparlisib overall exposure to sub-therapeutic levels.

Table 17. List of CYP450 Substrates to be used with caution

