APPENDIX B: Participant Eligibility Checklist

Protocol Title:	An open-label pilot study to evaluate the efficacy and safety of a combination treatment of Sonidegib and buparlisib for the treatment of advanced basal cell carcinomas
Protocol Number:	IRB-29839
Principal Investigator:	[name]

II. Subject Information:

Subject Name/ID:

Gender: Male Female

III. Inclusion/Exclusion Criteria

Inclusion Criteria			Supporting
	Yes	No	Documentation*

1. Age 18 years or older.		
2. Able to provide written informed consent obtained prior to any screening procedures		
3. Histologically documented diagnosis of basal cell carcinoma deemed to be locally advanced or metastatic		
4. ECOG performance status ≤ 2		
5. At least one measurable site of disease (as defined by Response Evaluation Criteria in Solid Tumors), or other disease specific response assessment criteria, as appropriate.		
State age restriction and/or gender/race-ethnic restrictions.		
6. Patients with adequate bone marrow, liver and renal function, as specified below:		
• Absolute Neutrophil Count (ANC) ≥ 1.5 x 10 ⁹ /L		
• Hemoglobin (Hgb) ≥ 9 g/dL		
• Platelets $\geq 80 \times 10^9/L$		
• Serum total bilirubin ≤ 1.5 x ULN (upper limit of normal)		
• AST and ALT ≤ 2.5 x ULN or ≤ 5 x ULN if liver metastases are present		
• Plasma creatinine phosphokinase (CK) \leq 1.5 x ULN		
• Serum creatinine ≤ 1.5 x ULN or 24-hour clearance ≥ 50 mL/min		
◆◆ CK > ULN		

Exclusion Criteria	Yes	No	Supporting Documentation*

Cohort 1 only: prior therapy with non- Sonidegib Smo Inhibitor	
2. Patients who have received prior treatment with a P13K inhibitor	
3. Patients with a known hypersensitivity to buparlisib or to its excipients	
4. Metastatic CNS tumors may participate in this trial, if the patient is ≤ 4 weeks from therapy completion (incl. radiation and/or surgery), is clinically stable at the time of study entry and is not receiving corticosteroid therapy	
5. Patients who have had major surgery within 4 weeks of initiation of study medication.	
6. Patients with concurrent uncontrolled medical conditions that may interfere with their participation in the study or potentially affect the interpretation of the study data.	
7. Patients unable to take oral drugs or with lack of physical integrity of the upper gastrointestinal tract or known malabsorption syndromes. State exclusion requirements due to co-morbid disease or incurrent illness, as needed.	

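### The eligibility rules for treated brain metastases conflict: the item 15 note admits corticosteroid users whom item 3 bars, and checklist item 4 does not carry the item 3 rule

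*Combined protocol and SAP*

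**What the plan says.** Section 3.2.2.2 is an exclusion list in which a patient must clear every item. Item 3 starts from "Patients with untreated brain metastases are excluded". It then lets patients with metastatic CNS tumors in "if the patient is > 4 weeks from therapy completion", provided the patient also "is clinically stable at the time of study entry and is not receiving corticosteroid therapy". There is no dose threshold and no reference to item 15.

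Item 15 of the same list excludes chronic steroid use. Its note makes an exception for patients with previously treated brain metastases on a stable low dose (examples given: dexamethasone 2 mg/day, prednisolone 10 mg/day). Those who have been on it "for at least 14 days before start of study treatment are eligible".

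Exclusion item 4 of the Appendix B checklist reads "Metastatic CNS tumors may participate in this trial, if the patient is ≤ 4 weeks from therapy completion". It then repeats the stability and no-corticosteroid conditions unchanged. The sentence on untreated brain metastases is absent, and no other checklist line names brain or CNS metastases. Checklist exclusion item 15 lists chronic steroids without the low-dose exception.

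Two other parts of the protocol deal with corticosteroids on study. Section 4.2.3.2 says "Concomitant treatment with corticosteroids and buparlisib should be avoided, whenever possible, during this study", allows short systemic courses of under 2 weeks, and warns that chronic dosing induces CYP3A and may lower buparlisib exposure. Table 14 in section 4.1.2.3.6 says of severe pneumonitis "Consider corticosteroids if infective origin is ruled out. Taper as medically indicated", with no 2-week limit.

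**The concern.** There are two separate faults in operative eligibility text.

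First, the body contradicts itself. A stable patient more than 4 weeks after brain treatment, on dexamethasone 2 mg/day for 14 days or longer, is barred by item 3 and called eligible by the item 15 note.

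Second, the checklist does not transmit the body rule. Appendix B ends in the statement that the subject is eligible or ineligible, so its wording matters for the decision. Item 4 sits under the exclusion heading but still speaks of who may take part, and its interval is the reverse of the one in the body.

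At stake are consistent enrolment decisions and the protection of patients recently treated for CNS disease. The corticosteroid question also has a pharmacological side, through the exposure warning in section 4.2.3.2, but the documents do not quantify that effect at low doses.

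**Working it through.** The protocol gives no figure to reproduce. The check compares the texts and counts which combinations each rule bars.

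**Corticosteroids, item 3 against the item 15 note.**

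- If the note is a free-standing statement of eligibility, it contradicts item 3.
- If the note only lifts item 15, it has no effect: everyone it describes has treated brain metastases and is on corticosteroids, so item 3 still bars them all.
- Checklist item 15 and the caution in section 4.2.3.2 favour item 3. That caution is not an absolute limit, as its own wording and Table 14 show. The note may therefore be a deliberate exception that was never written into item 3. The text does not settle which was meant.

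**Checklist item 4 against body item 3.** Take a patient with treated CNS metastases. Let A = 4 weeks or less since therapy, B = clinically stable, C = on corticosteroids. This gives 2 × 2 × 2 = 8 combinations. Body item 3 bars a patient if A, or not-B, or C. Item 4 can be read in three ways:

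- as a permission: admits A and B and not-C;
- as a literal exclusion: bars A and B and not-C;
- as an exclusion on the interval only: bars A.

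| Weeks since therapy | Stable | On corticosteroids | Body item 3 | Permission | Literal exclusion | Interval only |
|---|---|---|---|---|---|---|
| ≤ 4 | yes | no | barred | admitted | barred | barred |
| ≤ 4 | yes | yes | barred | silent | not barred | barred |
| ≤ 4 | no | no | barred | silent | not barred | barred |
| ≤ 4 | no | yes | barred | silent | not barred | barred |
| > 4 | yes | no | admitted | silent | not barred | not barred |
| > 4 | yes | yes | barred | silent | not barred | not barred |
| > 4 | no | no | barred | silent | not barred | not barred |
| > 4 | no | yes | barred | silent | not barred | not barred |

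Results:

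- Body item 3 bars 7 of 8 and admits 1.
- As a permission, item 4 expressly admits 1 of the 7 barred combinations and states no bar on the other 6.
- As a literal exclusion it bars 1, so it misses 7 − 1 = 6.
- As an interval-only exclusion it bars 4, so it misses 7 − 4 = 3.

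The count takes item 4 alone and treats item 3 as the body rule, without the low-dose exception. Untreated metastases lie outside the table; item 4 does not mention them.

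**A worked patient.** Consider a stable patient, off corticosteroids and recovered from side effects, 21 days after limited-field palliative brain radiation. Body item 21 reaches only "limited field radiation for palliation ≤ 2 weeks prior to starting study drug", and 21 > 14, so it does not apply. Body item 3 does, since 21 ≤ 28. On the checklist, exclusion items 11 and 20 also stop at 2 weeks, leaving item 4 as the only line that could stop enrolment. Read as a permission it lets the patient in; on either exclusion reading it stops the patient.

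**The case against.** The strongest reply is that both faults have a sensible default. Item 4 stands in an exclusion table with yes/no columns, and its interval was reversed as an exclusion requires, so a reader would probably take it as an exclusion. The worked patient is then stopped. The three combinations missed on the interval-only reading are patients who are unstable, on corticosteroids or both; checklist items 6 (uncontrolled conditions) and 15 (chronic steroids) may catch many of them. On corticosteroids, item 3 prevails because every exclusion must be cleared, so the note is redundant rather than unsafe. Section 3.2.2 also requires the principal investigator or a designee to review eligibility before enrolment, in a single-center study.

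Much of this stands, and it limits the consequence. It does not remove the fault. Even the most favourable reading of item 4 omits stability, corticosteroids and untreated disease, and the general items do not clearly cover short steroid courses or untreated metastases. The investigator doing the review would be working from contradictory text.

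It can also be said that the checklist departs from the body elsewhere, for example on AST/ALT limits, and sets both 4 and 2 weeks for prior surgery within itself. That is a reason to reconcile all of Appendix B; it does not cure this line.

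**Conclusion.** The concern holds: both texts are wrong as written. Items 3 and 15 give opposite answers for treated brain-metastasis patients on stable low-dose corticosteroids, and no reading of checklist item 4 reproduces item 3.

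The practical size is small. The study plans 12 + 12 = 24 patients (section 3.2.1), and few are likely to be affected. The documents give no rate of brain metastases or corticosteroid use, so no expected number can be stated. No effect on response rate or any other statistical quantity is shown. The counts of 1, 6 and 3 out of 7 describe rule combinations and rest on taking item 4 alone and item 3 as the body rule. Harm to a recently irradiated patient requires the permission reading; the omission of untreated metastases does not depend on the reading. This is a minor but clear drafting correction with some safety relevance.

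**What to change.** 1. Decide whether the low-dose exception is intended. If not, delete the brain-metastasis sentence from the note to item 15. If it is, write the same exception into item 3, section 4.2.3.2 and checklist exclusion items 4 and 15.
2. Replace checklist exclusion item 4 with a true exclusion, for example: *Untreated CNS metastases; or treated CNS metastases with any of the following: 4 weeks or less since the end of treatment (including radiation or surgery), not clinically stable, or receiving corticosteroids.* If the exception is kept, add it to the last clause. Without the exception, this wording bars A, or not-B, or C, so it agrees with item 3 in all 8 combinations by construction, and it restores the bar on untreated disease.

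The cost is wording only: one checklist line rewritten, plus one body sentence deleted or one exception copied into four places. Sample size, visits and analyses do not change.

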8. Patients who have neuromuscular disorders (eg, inflammatory myopathies, muscular dystrophy, amyotrophic lateral sclerosis and spinal muscular atrophy) or are on concomitant treatment with that are recognized to cause rhabdomyolysis, such as HMG CoA inhibitors (statins), clofibrate and gemfibrozil, and that cannot be discontinued at least 2 weeks prior to starting Sonidegib treatment. If it is essential that the patient stays on a statin to control hyperlididemia, only pravastatin may be used with extra caution.		
9. Patients who are planning on embarking on a new strenuous exercise regimen after initiation of study treatment. NB: Muscular activities, such as strenuous exercise, that can result in significant increases in plasma CK levels should be avoided whilst on sonidegib treatment		
10. Patients who have taken part in an experimental drug study within 4 weeks of initiating treatment with Sonidegib.		
11. Patients who are receiving other antineoplastic therapy (eg, chemotherapy, targeted therapy or radiotherapy) concurrently or within 2 weeks of starting treatment with sonidegib.		

12. Patients who are receiving treatment with medications known to be moderate and strong inhibitors or inducers of CYP3A4/5 or drugs metabolized by CYP2B6 or CYP2C9 that have narrow therapeutic index, and that cannot be discontinued before starting treatment with Sonidegib. Medications that are strong CYP3A4/5 inhibitors should be discontinued at least 7 days and strong CYP3A/5 inducers for at least 2 weeks prior to starting treatment with Sonidegib.	
13. Pregnant or nursing (lactating women, where pregnancy is defined as the state of a female after conception and until the termination of gestation, confirmed by a positive hCG laboratory test (> 5 mIU/mL).	

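### Exclusion 18 is a recovery instruction, not an exclusion, and conflicts with Appendix B item 11 on prior anticancer therapy; Appendix B also contradicts itself on major surgery

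*Combined protocol and SAP*

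**What the plan says.** The exclusion list in section 3.2.2.2 is introduced by the statement that patients "must not meet any" of its items. Item 18 describes patients given chemotherapy or targeted anticancer therapy in the last 4 weeks and then reads "6 weeks for nitrosourea, antibodies or mitomycin-C) prior to starting study drug must recover to a Grade 1 before starting the trial".

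The neighbouring items are built differently. Each names an exposure inside a window and adds non-recovery as a second ground for exclusion:
- Item 19: "continuous or intermittent small molecule therapeutics (excluding monoclonal antibodies) ≤ 5 effective half-lives prior to starting study drug".
- Item 21: "wide field radiotherapy ≤ 4 weeks or limited field radiation for palliation ≤ 2 weeks prior to starting study drug".
- Item 22: "22. Patients who have undergone major surgery ≤ 2 weeks".

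The Appendix B checklist, which ends in a signed statement of eligibility, does not carry item 18. Its item 11 excludes patients on other antineoplastic treatment ("chemotherapy, targeted therapy or radiotherapy) concurrently or within 2 weeks of starting treatment with sonidegib"). Its item 10 excludes "Patients who have taken part in an experimental drug study within 4 weeks of initiating treatment with Sonidegib". Its item 18 repeats the body's small-molecule rule, including the recovery clause. On major surgery, its item 5 says 4 weeks and its item 21 says 2 weeks.

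The footnote to Table 19 allows the baseline scan up to 28 days before treatment. Section 4.3.2 uses calipers for targets visible on the skin and imaging for the rest.

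**The concern.** Whoever confirms eligibility has two lists that can give different answers for the same patient, and the protocol does not say which governs. Someone working only from the checklist never sees item 18, so its Grade 1 condition and its 6-week class are lost. That is mainly a matter of safety and consistency at entry: residual toxicity from prior therapy could be carried into a two-drug combination. On major surgery the checklist alone gives two answers, and no interpretation is needed to see it.

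**Working it through.** No sample size, error rate or estimate is involved, and the plan states no figure to reproduce. The check sets the rules side by side. Days are counted back from the start of study drug: 2 weeks = days 1-14, 4 weeks = days 1-28, 6 weeks = days 1-42.

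**Item 18 against Appendix B item 11, these two items alone**

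| Patient | Item 18 as worded | Item 18 read as a washout | Appendix B item 11 |
|---|---|---|---|
| Chemotherapy 10 days ago, Grade 1 | passes | excluded | excluded |
| Chemotherapy 21 days ago, Grade 1 | passes | excluded | passes |
| Chemotherapy 21 days ago, Grade 2 | excluded | excluded | passes |
| Antibody 35 days ago, Grade 1 | passes | excluded | passes |
| Antibody 35 days ago, Grade 2 | excluded | excluded | passes |

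- As worded, the lists disagree in both directions. For a recovered patient the difference covers days 1-14, or 14 days. For a patient above Grade 1 it covers days 15-28 (28 - 14 = 14 days), or days 15-42 for nitrosourea, antibodies or mitomycin-C (42 - 14 = 28 days).
- Read as a washout, they differ over the same days 15-28 (14 days) or 15-42 (28 days), whatever the toxicity grade.

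**How far other items close the gap**

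- *Small molecules.* Body item 19 and Appendix B item 18 set the same 5-half-life limit, and both exclude patients not recovered from side effects, without stating a grade. With effective half-life h, the limit exceeds 14 days when h > 14/5 = 2.8 days, and 28 days when h > 28/5 = 5.6 days. The half-life of Cohort 2's prior non-sonidegib Smoothened inhibitor is not given, so its required interval cannot be worked out. The rule for it is nevertheless the same in both lists.
- *Chemotherapy.* If the person completing the checklist treats a chemotherapy drug as a small-molecule therapeutic, the recovery clause there may also catch the Grade 2 patient at day 21.
- *Antibodies.* The 5-half-life rule leaves them out in both lists, so the day-35 Grade 2 case stands.
- *Investigational agents.* Appendix B item 10 holds them back for 4 weeks, which covers days 15-28 but not 29-42.
- *Other cancers.* Exclusion 26 bars "History of another malignancy within 3 years, except cured basal cell carcinoma of the skin or excised carcinoma in situ of the cervix". An antibody would therefore mostly have been given for BCC, and the prior BCC drug therapy the protocol describes is Smoothened inhibitor monotherapy.

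**Major surgery**

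At 21 days, Appendix B item 5 excludes; Appendix B item 21 and body item 22 do not. The disagreement covers days 15-28, or 14 days.

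**Baseline scan (a separate point, not a conflict between the lists)**

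Both lists let limited-field radiation end on day -15. A scan on day -28 would precede its end by 28 - 15 = 13 days. A scan on day -21, where Table 19 places screening, would precede it by 21 - 15 = 6 days. Only imaged targets are concerned.

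**The case against.** The strongest reply is that the lists can be applied together. Section 3.2.2 requires every criterion to be satisfied, so a patient who must pass both lists meets the stricter limit, and no recently treated patient slips in. This is a sensible practice, but it is an inference: the protocol does not state it.

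A second reply is that recovery to Grade 1 is a legitimate entry rule in its own right. It is, but the stated windows then exclude no recovered patient, and the checklist carries neither the grade nor the windows. Reading the lead-in so that item 18 becomes a plain washout leaves its recovery clause without meaning and still contradicts the 2 weeks in the checklist.

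A third reply concerns consequence. A reader might infer that shrinkage from earlier therapy will be credited to the combination. With 12 patients per cohort and no control arm, one misattributed response would move a cohort's response rate by 1/12 = 8.3 percentage points. The documents do not support expecting this. Cohort 1 is naive to Smoothened inhibitors; Cohort 2 enters because disease was refractory or relapsed on one; small molecules must clear 5 half-lives in both lists; and no antibody or chemotherapy for BCC is described. Section 4.2.3 also requires prior therapy within 4 weeks to be recorded, so most such cases could be identified afterwards, except at days 29-42 for the 6-week agents. This objection stands.

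Finally, a hard 4-week washout on all targeted therapy could reach Cohort 2's defining prior drug, and so up to all 12 of its patients, who have few alternatives. This also stands and shapes the fix.

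**Conclusion.** The point holds as a minor drafting fault in operative eligibility rules. Item 18 does not work as an exclusion, and it disagrees with Appendix B item 11 on either reading: over days 1-14 for a recovered patient and days 15-28 (15-42) for an unrecovered one as worded, or over days 15-28 (15-42) as a washout. Appendix B contradicts itself on surgery over days 15-28. The clearest case is a patient 35 days after an antibody with residual Grade 2 toxicity, whom item 18 bars and Appendix B items 11 and 18 do not.

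The conclusion rests on the two texts as printed and on the absence of any statement of which list governs. The number of patients affected is not given; it is probably small and could be zero. No bias in the response rate is shown. The radiation and scan timing is a separate, optional improvement with a worst case of 13 days; the documents do not say that palliative radiation would be given to a target lesion.

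**What to change.** Put one text in both lists, in the form of items 19, 21 and 22: exclude patients who received chemotherapy, an antibody or other targeted anticancer therapy within 4 weeks before study drug (6 weeks for nitrosourea, antibodies or mitomycin-C), or who have not recovered to Grade 1. State that targeted small molecules, including a prior Smoothened inhibitor, are governed by the shared 5-half-life rule plus recovery to Grade 1, so that Cohort 2 does not acquire a new fixed washout. In Appendix B this text replaces the 2 weeks for drug therapy in item 11. Keep that item's bar on concurrent therapy, and leave radiation to item 20. Choose one interval for major surgery and use it in Appendix B items 5 and 21 and in body item 22.

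Separately, require the baseline scan of an imaged target to be taken after the last prior anticancer therapy.

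The cost is protocol and checklist wording. A few patients would wait longer or be scanned later.
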